COVER PAGE

Peri-implant Phenotype, Calprotectin and Mmp-8 Levels in Cases Diagnosed With Periimplant Disease

[name] DDS, PhD¹, [name] DDS, PhD²

¹Bilecik Şeyh Edebali University, Faculty Of Dentistry, Department of Periodontology, Bilecik, Turkey

²Van Yuzuncu Yıl University, Faculty of Dentistry, Department of Periodontology, VAN,

Turkey

Corresponding Author: [name]

Address: Bilecik Şeyh Edebali University, Faculty Of Dentistry, Department of

Periodontology, [name]

E-mail address: [contact] [contact] Office [contact]

[name]

Bilecik Şeyh Edebali University, Faculty Of Dentistry, Department of Periodontology, [name]

E-mail address: [contact] [contact] Office [contact]

[name]

Van Yuzuncu Yıl University, Faculty of Dentistry, Department of Periodontology, VAN,

Turkey

E-mail address: [contact] [contact]

STUDY PROTOCOL AND STATISTICAL ANALYSIS PLAN

Aim of Research: In this study, it was aimed to investigate the effect of peri-implant soft tissue phenotype on the degree of peri-implant disease and its contribution to the results of non-surgical mechanical treatment, accompanied by clinical and biochemical parameters. The research hypothesis is that better clinical outcomes may be achieved in individuals with thicker soft tissue phenotype.

Scientific Basis and Validity of Medical Research:

Over the last two decades, dental implants have been used to replace missing teeth; It has become a widely accepted and applied therapeutic method to support fixed and removable prostheses (1). A dental implant is generally defined as a root form made of titanium that is placed in place of a natural tooth (2).

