The patients to be included in the research will be selected among 50 volunteer individuals aged between 18-65 who applied or were referred to Van Yüzüncü Yıl University Faculty of Dentistry Department of Periodontics with complaints of inflammation in the peri-implant area and were diagnosed with peri-implantitis disease. People who have systemic diseases, smokers, have used antibiotics or received any other medical treatment within 6 months, and are pregnant or breastfeeding will be excluded from the study. Additionally, individuals who

met the definition of peri-implant health and individuals who required surgical treatment of peri-implantitis were excluded from the study.

The peri-implant soft tissue phenotype of all participants who are detected to have periimplant disease and will be included in the study will be measured, necessary clinical and radiological examinations will be performed, necessary samples will be collected and conventional mechanical treatments will be applied. The data of all participants will be collected again in the 6th month following the treatment.

Patient Data Records, Peri-implant Disease Treatment

The details of the application and the research to be conducted will be explained to the patients who will participate in the study, and an informed consent form will be signed. Patients diagnosed with peri-implant disease will be asked for routine examinations before treatment, intraoral photographs will be taken, and clinical and radiological examinations will be performed in detail. Detailed anamnesis of patients who meet the selection criteria will be taken and clinical and radiological examinations will be performed. Patients with caries on their teeth will be directed to Restorative Dentistry Department and restorations of existing caries will be made at the relevant clinic. Before starting their treatment, patients who meet the selection criteria will be given detailed information about periodontal and peri-implant diseases, microbial dental plaque that causes these diseases, and methods of preventing microbial dental plaque. Individuals will be taught how to brush their teeth, how to use an interdental brush.

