If the millimetric values obtained as a result of measurements are less than 1 mm, thin phenotype; If it is more than 1 mm, it will be classified as thick phenotype (15). The second gingival phenotype evaluation in individuals with peri-implant disease will be performed with the Hu-Friedy Colorvue Biotip Probe[®], a newly developed probe with a colored tip that will be placed in the peri-implant pocket. The white probe will first be placed in the peri-implant pocket with a pressure of less than 25 N. If the color of the probe reflects from the gingival tissue, the phenotype will be recorded as thin. If the white color is not visible, the green probe will be placed in the pocket in the same way and if the color is reflected, the phenotype will be classified as medium thickness. If the Green tip is not visible through the gingival tissue, the Blue probe will be used and if the only color seen is Blue, the phenotype will be classified as thick. If blue is not visible, the peri-implant mucosa tissue will be recorded as too thick. Then, traditional mechanical debridement with titanium curettes will be applied to the areas with peri-implant disease without losing the effect of anesthesia. The area will be irrigated with physiological saline from time to time. Following the procedure, patients will be called for control at the 1st, 3rd and 6th months. Oral hygiene instructions will be repeated when necessary. At the 6th month, all clinical parameters examined will be measured again and PIOS samples will be collected again. 6th month following the operation; PIOS samples will be collected again from all operated patients and the clinical parameters examined will be recorded.

Immunohistochemical Analysis

After the target number of patients is reached, the PICF samples collected will be sent to the laboratory for analysis using ELISA (Enzyme-linked immunosorbent assay) kits.

Statistical analysis

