Descriptive statistics for the features emphasized will be expressed as Median, Average, Standard Deviation, Minimum and Maximum value. In terms of these characteristics, two-factor and one of the factors repeated-measures analysis of variance will be used to compare group averages and periods (0th month and 6th month). To determine the relationship between variables, Pearson or Spearman correlation coefficients will be calculated separately in the groups. In the calculations, the statistical significance level will be taken as 5% and the SPSS statistical package program will be used for the calculations.

Figure- 1. Clinical Index Form

PLAQUE INDEX

REFERANCES

1 COSGAREA, Raluca; SCULEAN, Anton; SHIBLI, Jamil Avad And SALVI, Giovanni Edoardo. Prevalence Of Peri-İmplant Diseases – A Critical Review On The Current Evidence. Braz. Oral Res. [Online]. 2019, Vol.33, Suppl.1, E063. Epub Sep 30, 2019. ISSN 1807-3107.

5. Caton, J. G., Armitage, G., Berglundh, T., Chapple, I. L. C., Jepsen, S., Kornman, K. S., ... Tonetti, M. S. (2018). A new classification scheme for periodontal and peri-implant diseases and conditions - Introduction and key changes from the 1999 classification. Journal of Clinical Periodontology, 45, S1–S8. doi:10.1111/jcpe.12935

6. NOVAES JUNIOR, Arthur Belém et al. New strategies and developments for periimplant disease. **Braz. oral res.**, São Paulo , v. 33, supl. 1, e071, 2019 . access on 09 June 2020. Epub Sep 30, 2019.

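### Correlations are planned only within groups, with no overall estimate and no test between groups, which costs power and leaves no planned basis for a group-specific claim

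*Combined protocol and SAP*

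**What the plan says.** The Statistical analysis section has one sentence on associations: "Pearson or Spearman correlation coefficients will be calculated separately in the groups". It adds that "the statistical significance level will be taken as 5" per cent, without saying whether tests are two-sided. It mentions no overall coefficient, no group-adjusted coefficient, no interaction and no comparison of coefficients.

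The only between-group analysis is a two-factor analysis of variance with one repeated factor, which "will be used to compare group averages and periods (0th month and 6th month"). That compares means, not associations.

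The section does not say what the groups are. The hypothesis under Aim of Research is that "better clinical outcomes may be achieved in individuals with thicker soft tissue phenotype", which points to phenotype. The section on patient data records and treatment gives two phenotype rules:

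- Transgingival probing has two classes, cut at 1 mm: "If it is more than 1 mm, it will be classified as thick phenotype".
- The colour probe has four classes, the last being: "If blue is not visible, the peri-implant mucosa tissue will be recorded as too thick".

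The same section says that the two techniques will be correlated with each other, and mentions no split by group there. On sample size, patients are "selected among 50 volunteer individuals aged between 18-65". No split, expected correlation or power is given.

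**The concern.** Two things are at stake.

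- **Power.** If a biomarker and a clinical index are related in much the same way in thin and thick tissue, splitting the sample tests that one relation twice, each time on a fraction of the patients. Group sizes are whatever recruitment delivers, so one group may be very small.
- **Interpretation.** The study asks what phenotype does, with biochemical measures alongside. Coefficients listed by group, each with its own p-value, invite the reading that a relation exists in one phenotype and not in the other. One significant and one non-significant result do not show a difference, and the plan provides no analysis that could.

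**Working it through.** **The plan's own figure.** There is no calculation to reproduce. The number 50 has no effect size, standard deviation or power behind it.

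**Inputs.**

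- From the documents: 50 people and a 5% level.
- Assumed: all 50 are analysed, with one independent observation each; tests are two-sided; there are two groups; the true r is the same in both; data are bivariate normal.
- Varied, because the documents give neither: r from 0.2 to 0.7, and splits of 25/25, 15/35 and 10/40.

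**Power per group.** With Fisher's z, power ≈ Φ(atanh(r)·√(n−3) − 1.96); the other tail is negligible here. For r = 0.40 and n = 25: atanh(0.40) = 0.4236, times √22 = 4.690, gives 1.987; less 1.96 gives 0.027; Φ = 0.51. Simulation of the t-test of r (60,000 runs) gives 52-53%. At n = 10 power is only 20-22%.

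**Power over all 50, adjusted for group.** Replace √(n−3) by √(50−4) = 6.782. Then 0.4236 × 6.782 = 2.873; less 1.96 gives 0.913; Φ = 0.82. Simulation gives 83% for Pearson and about 78% for the partial Spearman proposed under the fix. The like-for-like Pearson comparison is therefore about 52% against 83%.

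**Smallest significant |r|.** It is 0.396 at n = 25 and 0.632 at n = 10, against 0.279 at n = 50.

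**Chance that exactly one group is significant.** For independent groups with powers p₁ and p₂ this is p₁(1−p₂) + p₂(1−p₁). At 25/25 and r = 0.40: 2 × 0.511 × 0.489 = 0.50. At 10/40: 0.202 × 0.269 + 0.731 × 0.798 = 0.64. Simulated values in per cent:

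| Split | r = 0.2 | 0.3 | 0.4 | 0.5 | 0.6 | 0.7 |
|---|---|---|---|---|---|---|
| 25/25 | 27.1 | 42.8 | 49.6 | 38.2 | 15.9 | 3.0 |
| 15/35 | 27.6 | 45.1 | 56.3 | 49.5 | 30.6 | 12.3 |
| 10/40 | 28.2 | 48.0 | 63.5 | 64.5 | 51.2 | 32.0 |

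A Fisher z test between the two groups wrongly declares a difference in 4.7-5.2% of the same simulated trials.

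**What the direct test can detect.** At 25/25 the standard error is √(1/22 + 1/22) = 0.3015. For 80% power the difference in z must be 2.80 × 0.3015 = 0.844, and tanh(0.844) = 0.69, that is r = 0.69 against 0. At 10/40, √(1/7 + 1/37) = 0.412, and tanh(2.80 × 0.412) = 0.82. Power for 0.40 against 0 at 25/25 is 29%.

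**Relations that involve thickness.** If the groups are thickness cut at 1 mm, splitting also restricts the range of thickness. Take a normal variable cut at its median and a true r of 0.40. The variance within each half is 1 − 2/π = 0.363 of the whole (SD ratio 0.603), so the within-group r is 0.40 × 0.603 / √(0.84 + 0.16 × 0.363) = 0.25. Power is then about 23% per group of 25. Adjusting for phenotype group does similar harm: in simulation at N = 50, Spearman falls from 0.38 to 0.23 and power from 79% to about 36%. These relations need an overall estimate without that adjustment.

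**The case against.** A reader might infer that a relation shared by both groups will look group-specific about half the time. The documents do not support that in general. With equal groups, 2p(1−p) cannot exceed 50%, and it comes near that only around r = 0.40. At 25/25 it is 27% at r = 0.2, 16% at 0.6 and 3% at 0.7, and it passes half only with unequal groups. The plan states no expected r.

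A reader might also infer that the investigators will report relations as holding in one phenotype only. The plan says that coefficients will be calculated; it does not say that significance will be compared across groups. Anyone given the coefficients and group sizes could run a Fisher z test. What stands is that the plan neither prevents the invalid comparison nor provides the valid one.

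Three further points against the concern have force.

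- Two phenotype groups is an inference. Under the four-class rule the average group would be 50/4 = 12.5 people, which makes the power problem worse but changes the figures. The wording also leaves open whether 50 is the enrolled number or the pool selected from. Strips are taken from each implant, so the unit of analysis might be the implant.
- Not every correlation is clearly split: the comparison of the two measuring techniques is described without groups.
- The main hypothesis is addressed by the analysis of variance, and within-group coefficients do guard against mixing in differences between group means. A group-adjusted coefficient keeps that protection without the loss of power.

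**Conclusion.** The concern holds in conditional form. Correlations are planned only within undefined groups, with no overall estimate and no test between groups. Assuming 50 patients, a 25/25 split and a true r of 0.40, this leaves about 52% power per group where one group-adjusted coefficient would have about 78% (Spearman) to 83% (Pearson).

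The plan also contains no valid basis for a statement that a relation holds in one group only. If significance were used for that purpose, a shared r of about 0.3 to 0.5 would mislead about 38-50% of the time at 25/25 and about 45-65% at 15/35 to 10/40, and less often for weaker or stronger r. A direct test would mislead about 5% of the time.

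All these figures rest on assumed splits and correlations, two groups and one observation per patient. The power gain supposes that the relation is similar in both groups; if it is not, the overall coefficient is an average. These are secondary analyses, so this is a change that should be made, but it does not undermine the main comparison.

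**What to change.** Name the grouping variable in the Statistical analysis section, and replace the correlation sentence with text to this effect:

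- Each relation that does not involve mucosal thickness or phenotype is estimated once over all participants, as a partial Spearman correlation (regression on ranks) adjusted for group.
- Relations that involve thickness or the colour-probe class, including the comparison of the two measuring techniques, are estimated over all participants without adjustment for phenotype group.
- Within-group coefficients are descriptive and reported with 95% confidence intervals.
- A difference between groups is claimed only from a group-by-variable interaction or a Fisher z test.

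The plan should state the downside: at 25/25 the difference test reaches 80% power only for about r = 0.69 against 0, and at 10/40 for about 0.82 against 0. A non-significant result is therefore not evidence that the groups are alike. The cost is a few sentences and a few lines of analysis code, with no new data.

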Peri-implant crevice fluid (PIOS) samples will be collected from all individuals before proceeding with mechanical treatment of diseased implant sites. The areas will be isolated from saliva with cotton pellets, dried with light air, and paper strips (PerioPaper®) will be kept in the trough for 30 seconds (13). Paper strips obtained from each implant will be placed in Eppendorf tubes containing isotonic Ph:7.4 phosphate buffer solution and stored at -40 ° C until analyzed in the laboratory department of our clinic. Routine periodontal parameters such as plaque index (PI) (14), gingival index (GI) (14), bleeding on probing and probing pocket depth scores of the patients whose PIOS samples are collected will be recorded with a Williams-type plastic probe. Following these procedures, the patients' peri-implant phenotype will be evaluated. In the evaluation, the traditional transgingival probing technique and a newly developed technique will be used simultaneously and their correlations with each other

will be examined. A digital caliper with a sensitivity of 0.01 mm will be used to measure transgingival probing values to determine peri-implant mucosa thickness. Measurements will be made from two points: apical of the free gingival sulcus and coronal of the mucogingival junction. After the peri-implant mucosa thickness measurement points are determined with a marker pen, Xylocaine® spray (Vemcaine 10%, lidocaine) or, if necessary, local anesthetic (Maxicaine, lidocaine hydrochloride) will be applied to prevent the patient from feeling pain. Measurements will be made from the marked points in a direction perpendicular to the peri-implant mucosa, using a 10-gauge endodontic spreader (G-Star Medical Co., Ltd., Guangdong, China) with a silicone stopper until its contact with the alveolar bone is felt. Since excessive force will cause the spreader to exceed the soft tissue and advance in the alveolar bone, care should be taken to apply only light forces that can be limited to the soft tissue. After all measurements are repeated twice by the same researcher at 10-minute intervals, the amount of peri-implant mucosa thickness in each region will be determined by taking the average of the two measurements.

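### No outcome or contrast is primary and every test uses 5%, so a false phenotype finding is well above nominal: about 13-19% for four clinical outcomes, 16-27% for six, under stated assumptions

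*Combined protocol and SAP*

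**What the plan says.** The Aim of Research gives one hypothesis, that "better clinical outcomes may be achieved in individuals with thicker soft tissue phenotype". It does not say which outcome, time point or comparison settles it.

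Under Patient Data Records, Peri-implant Disease Treatment, four clinical measures are named, in a list that is left open: "Routine periodontal parameters such as plaque index (PI) (14), gingival index (GI) (14), bleeding on probing and probing pocket depth scores". The title adds two biomarkers: "Peri-implant Phenotype, Calprotectin and Mmp-8 Levels in Cases Diagnosed With Periimplant Disease". The Immunohistochemical Analysis section says that "PICF samples collected will be sent to the laboratory for analysis using ELISA" but does not list the analytes.

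Phenotype is classified in two ways: thin or thick at a 1 mm cut-off by transgingival probing, and four categories by colour probe. The plan does not say which one is the group factor.

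The Statistical analysis section states that "two-factor and one of the factors repeated-measures analysis of variance will be used to compare group averages and periods (0th month and 6th month"). It adds Pearson or Spearman correlations within each group, without limiting their number, and then sets the level: "In the calculations, the statistical significance level will be taken as 5" per cent. It names no primary outcome, primary contrast, multiplicity adjustment or exploratory label.

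**The concern.** One hypothesis is to be judged from several tests, each at 5%, with no rule for combining them. Each mixed ANOVA yields two tests that involve phenotype: the group effect, averaged over both periods, and the group-by-period interaction, which compares change. Either could be read as the answer, for any of four to six outcomes.

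The stated 5% then describes each test but not the conclusion that the study wants to draw. With nothing fixed in advance, a chance result on one index could be presented as evidence that thick phenotype does better, and a reader of the report could not tell how many other results might have served.

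**Working it through.** **Inputs from the document.** Per-test level 5%; four named clinical outcomes; two biomarkers in the title; two periods (0 and 6 months); 50 patients.

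**Assumptions (not in the document).** No true phenotype effect on any outcome; equal correlation r between outcomes, varied from 0 to 0.9; two-sided tests, since ANOVA F tests are non-directional; group splits of 25/25 or 15/35.

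**The plan's own figure.** The 5% is a chosen per-test level, so there is nothing to derive. One test alone gives 5.0%, or 2.5% in the direction of the hypothesis.

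**1. At least one false difference, either direction, one contrast per outcome.** For k independent tests the chance is 1 − 0.95^k:
- k = 4: 1 − 0.95⁴ = 18.5%
- k = 6: 1 − 0.95⁶ = 26.5%

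For correlated tests it is 1 − P(all |Zᵢ| < 1.96), with equicorrelated normal Zᵢ, by numerical integration:

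| r | 4 outcomes | 6 outcomes |
|---|---|---|
| 0 | 18.5% | 26.5% |
| 0.3 | 17.4% | 24.1% |
| 0.5 | 15.6% | 20.7% |
| 0.7 | 13.0% | 16.4% |
| 0.9 | 9.4% | 10.8% |

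A simulation of the two-group, two-period design (50 patients, both splits, assumed pre/post correlation 0.5) gave about 17% to 27% for six outcomes with r from 0.7 to 0, in agreement.

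**2. Both phenotype tests counted.** Six outcomes × 2 tests = 12 tests. If independent, 1 − 0.95¹² = 46.0%. The same simulation gave about 46% at r = 0, 38% at 0.5 and 30% at 0.7.

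**3. False results favouring thick phenotype only.** Each two-sided 5% test has a 2.5% chance in that direction. For independent tests the chance is 1 − 0.975^k:
- k = 4: 9.6% at r = 0, 8.7% at 0.3, 7.8% at 0.5, 6.5% at 0.7
- k = 6: 14.1% at r = 0, falling to 8.2% at 0.7

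The comparator is 2.5%.

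**4. After a fix.** One named outcome and contrast: 5.0%. For Holm over six, the first step uses 0.05/6 = 0.0083; six independent tests at that level give 1 − (1 − 0.0083)⁶ = 4.9%, and less if correlated.

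**5. Price of Holm over six.** Smallest standardised difference detectable with 80% power, two-group comparison, noncentral t:

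| Split (assumed) | level 0.05 | level 0.05/6 |
|---|---|---|
| 25/25 | 0.81 SD | 1.02 SD |
| 15/35 | 0.88 SD | 1.11 SD |

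**The case against.** The strongest reply is that the plan never promises more than a per-test level. That is correct. A reader might infer that the plan contains a rule under which any one significant result among six confirms the hypothesis, or that it claims a 5% error rate across all tests. It contains neither. It is silent on how results combine, and the concern rests on that silence.

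Second, the hypothesis is directional and speaks of clinical outcomes, while the aim mentions clinical and biochemical parameters separately. The strict family may therefore be four outcomes, and only false results favouring thick phenotype would wrongly support the hypothesis. That gives 6.5-10%, not 16-27%. This stands as a limit on the size, but 6.5-10% is still about three to four times the 2.5% of a single test (6.5/2.5 = 2.6; 9.6/2.5 = 3.8).

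Third, the ranges depend on correlations that the document does not give and on an outcome list that is left open. This also stands, and no single figure should be quoted without its conditions.

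A reader might go further and count 6 × 3 = 18 ANOVA effects plus 84 pairwise correlations, and so expect about five false positives. The document does not support this. It fixes neither the number of variables nor the pairs. Many of the correlations would be real if outcomes are correlated. Change over time is plausible too, because every patient is treated between the two measurements.

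Last, a 50-patient study with a tentatively worded hypothesis could reasonably be wholly exploratory. If that is the intention, the plan should say so; at present it pairs a directional hypothesis with a significance level.

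**Conclusion.** The point holds as a missing decision rule. With no true phenotype effect, the chance of at least one false phenotype difference is above 5% in every scenario tried. With one contrast per outcome and r between 0.7 and 0, it is about 13-19% for the four clinical outcomes and 16-27% for six; at r = 0.9 it is still about 11% for six. Leaving the contrast open as well raises the figure for six outcomes to about 30-46%. In the direction of the hypothesis, the rates are about 6.5-10% and 8-14% against 2.5%. Using both phenotype classifications, or drawing claims from the correlations, would add further opportunities that are not counted here.

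The plan should be changed. The wording is cheap to correct, but the choice is credible only if it is made before the data are seen.

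**What to change.** In Statistical analysis, before data are seen, name one primary clinical outcome, one phenotype classification and one contrast that the planned ANOVA delivers, and test it at 5%. An example is the group-by-period interaction for probing pocket depth, thin versus thick at the 1 mm cut-off. A plain 6-month thick-versus-thin comparison is not an effect of that ANOVA; if it is preferred, the analysis model must be changed to match.

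Label the other outcomes and all correlations exploratory and report them as estimates with 95% confidence intervals. Alternatively, apply Holm to the other phenotype contrasts as a separate secondary family.

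If the team does not wish to choose one outcome, fix the classification and the contrast and apply Holm across all six outcomes.

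**Cost.** The change is to wording only, with no extra patients, visits or measurements. A named primary contrast keeps the full 5% and loses no power. Holm across six raises the first-step detectable difference at 80% power from 0.81 to 1.02 SD at a 25/25 split, or from 0.88 to about 1.11 SD at 15/35. Both splits are assumed: phenotype is observed, not allocated, so the actual split is unknown until patients are measured.
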